4.7.1.3. Events Causing Death

The observation periods for patient deaths are per the observation periods defined above.

- Death on-treatment: deaths occurring during the TEAE period,
- Death post-treatment: deaths occurring during the post-treatment period.

4.7.2. Clinical Laboratory Safety Variables

Clinical laboratory tests will consist of blood analyses (including hematology and clinical chemistry) and urinalysis. Clinical laboratory values will be converted and analyzed in international units, including associated normal ranges provided by the central laboratory. International units will be used in all listings and tables. Clinical laboratory values in conventional (US) units will also be available in the database, with associated normal ranges (analyses can be provided upon request). Both actual test values and "change from baseline" values (defined as the post-baseline value minus the baseline value) will be used in the result summaries. Potentially clinically significant abnormalities (PCSA) ranges will be applied to the laboratory test values as applicable (see Appendix 10.2 for PCSA definitions).

Unless otherwise specified below, blood samples for clinical laboratories will be collected at the protocol scheduled visits, and visits will be assigned to the Analysis Windows (See Appendix 10.1). The laboratory parameters (excluding those considered as efficacy parameters) will be classified as follows:

- Hematology:
 - Red blood cells and platelets: hemoglobin, hematocrit, erythrocytes count, platelets count, reticulocyte count, ery. mean corpuscular Hemoglobin (MCH), ery. mean corpuscular HGB concentration (MCHC), ery. mean corpuscular volume (MCV)
 - White blood cells: white blood cell count, neutrophils, lymphocytes, monocytes, basophils, eosinophils
- Clinical chemistry:
 - Metabolism: glucose, total protein, albumin, creatine phosphokinase
 - Electrolytes: sodium, potassium, chloride, calcium, phosphorus, bicarbonate
 - Renal function: creatinine, creatinine clearance, blood urea nitrogen (BUN), uric acid
 - Liver function: alanine Aminotransferase (ALT), aspartate aminotransferases (AST), alkaline phosphatase (ALP), GGT, bilirubin, LDH
- Hepatitis screen: anti-hepatitis-C antibody and hepatitis B surface antigen collected at day 1 and week 192.

4.7.3. Vital Sign Variables

Vital signs parameters will include height (cm), weight (kg), heart rate (bpm), systolic and diastolic blood pressure (mmHg) after resting at least five minutes. Both actual test values and "change from baseline" values (defined as the post-baseline value minus the baseline value) will be provided for protocol specified visits and visits will be assigned to the Analysis Windows (See Appendix 10.1). Potentially clinically significant Abnormalities (PCSA) ranges will be applied to the vital sign parameter values as applicable (see Appendix 10.2 for PCSA definitions).

4.8. Other Variables

The other endpoints of the study will include:

- The percent change in hs-CRP from baseline to protocol specified visits. Hs-CRP values greater or equal to 10 mg/L will be excluded from analyses in a second approach, since these are suggestive of concurrent infection(1). PCSA (potentially clinically significant abnormalities) criteria for hs-CRP are listed in Appendix 10.2.
- The absolute change in HbA1c (%) from baseline to protocol specified visits. PCSA criteria for HbA1c are listed in Appendix 10.2.
- The proportion of patients with two consecutives results, separated by at least 21 days, of calculated LDL-C <25 mg/dL (<0.65 mmol/L) (and again for calculated LDL-C <15 mg/dL [< 0.39 mmol/L]) during the treatment period.
- For the patients with two consecutive results as described above, the time to the first calculated LDL-C <25 mg/dL (<0.65 mmol/L) (and again for calculated LDL-C <15 mg/dL [< 0.39 mmol/L]) during the treatment period.

Protocol schedule visits will be assigned to the Analysis Windows (See Appendix 10.1).

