5.7. Analysis of Safety Data

The summary of safety results will be presented on the safety population (Section 3.1). No formal inferential testing will be performed. Summaries will be descriptive in nature. All summaries of safety results described below will be presented for each period respectively, unless otherwise noted.

General common rules

All safety analyses will be performed, unless otherwise specified, using the following common rules:

- Safety data in patients who do not belong to the safety population (i.e., exposed but not enrolled) will be listed separately.
- The baseline value will be defined as the last available value before the first dose of double-blind study treatment in the neurocognitive function study (R727-CL-1532).
- PCSA values are defined as abnormal values considered medically important by the Sponsor according to predefined criteria/thresholds based on literature review and defined by the Sponsor for clinical laboratory tests and vital signs (PCSA version dated January 2009 [Appendix 10.3]). Considering that the threshold defined in the PCSA list for monocytes and basophils can be below the ULN, the following PCSA criterion will be used for the PCSA analysis of monocytes and basophils:
 - PCSA criterion for monocytes: >0.7 Giga/L or >ULN (if ULN ≥ 0.7 Giga/L).
 - PCSA criterion for basophils: >0.1 Giga/L or >ULN (if ULN ≥ 0.1 Giga/L).

- PCSA criteria will determine which patients had at least 1 PCSA during the TEAE period, taking into account all evaluations including nonscheduled or repeated evaluations.
- The treatment-emergent PCSA denominator for a given parameter will be based on the number of patients assessed for that given parameter at least once during the TEAE period.
- All measurements, scheduled or unscheduled, fasting or not fasting, will be assigned to analysis windows defined in Appendix 10.1, Table 1 in order to provide an assessment for week 8 to week 96 time points.

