5.7.2. Analysis of Clinical Laboratory Variables

Clinical laboratory parameter actual values (quantitative) and change from baseline values will be descriptively summarized at baseline and each post-baseline visit (collected up to the day of last dose of study treatment +21 days) by at least patient number, mean, median, Q1, Q3, SD, minimum and maximum for each patient group. Additionally, laboratory parameter measures for last on-treatment values and worst on-treatment values will be summarized in a similar manner. Clinical laboratory parameters mean changes from baseline, with the corresponding SE, can be plotted at each visit, in the case results warrant further investigation. These parameters will be presented by the biological functions defined in Section 4.7.2. For glucose, only fasting samples will be included in the summaries.

Individual patient laboratory parameter measurements will be additionally evaluated by PCSA criteria, specifically identifying patients with at least one post-baseline measurement that meets the PCSA criteria within the TEAE period. The following additional project specific PCSA criteria will also be evaluated during the TEAE period:

- Patients with a hemoglobin decrease from baseline ≥ 15 g/L.
- Patients meeting the ALT increase defined in Section 4.7.1.2.
- Glucose (quantitative summary and PCSA) will also be analyzed, overall and according to the diabetic status at baseline.

Patients meeting the PCSA criteria at least once will be summarized by patient count (and percent) for a post-baseline PCSA measurement while accounting for the baseline PCSA status (PSCA normal/missing; PCSA abnormal), for each patient group. For the appendix, this laboratory parameter PCSA table will be reproduced with patients meeting the PCSA criteria at least once during the TEAE period regardless of baseline PCSA status. These laboratory parameters will be presented by the biological functions defined in Section 4.7.2. Patient listings of laboratory measurements that meet PCSA criteria will be provided for the report appendix. For those laboratory parameters that don't have an associated PCSA criteria, similar summary tables can be provided based on measurements outside the central laboratory normal ranges, if applicable.

Drug-induced liver injury

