5.8. Analysis of Other Variables

The summary of other variables will be presented on the safety population. No formal inferential testing will be performed for either period. Summaries will be descriptive in nature.

All measurements, scheduled or unscheduled, fasting or not fasting, will be assigned to analysis windows in order to provide an assessment for week 8 to week 96 time points.

Hs-CRP and HbA1cparameters (Section 4.8) will be summarized for the number of patients with data, mean, SD, median, minimum, and maximum (for hs-CRP, Q1 and Q3 will be also provided) by analysis visit during the treatment period. For HbA1c, summaries will also be provided according to diabetes mellitus status at baseline. The time profile will be plotted for HbA1c showing the means and the corresponding SEs, while medians (with Q1-Q3) will be plotted for hs-CRP. Applying the PCSA criteria to these variables at any time during the TEAE period, the number of patients (and percentages) meeting the criteria will be summarized.

The gonadal hormone parameters (Section 4.6.2) will be summarized for the number of patients with data, mean, SD, median, minimum, and maximum by analysis visit during the treatment period. For FSH and LH, the summaries will be performed for all patients, female patients, and male patients. Estradiol will be summarized for female patients only, and testosterone will be summarized for male patients only. Summary tables will also be provided for gonadal hormone parameters based on measurements outside the central laboratory normal ranges, if applicable. When appropriate, for female patients the gonadal-gonadotrophin in menopausal and non-menopausal women will be summarized separately.

In order to minimize confounding factors with menopause or exogenous estrogens, the summaries of estradiol, FSH, and LH for female patients will be repeated by excluding patients who were receiving hormone replacement therapy, were \geq 50 years, or had FSH levels \geq 25 IU/L at baseline.

For male patients, the summaries of testosterone, FSH, and LH will be repeated by excluding patients who were receiving testosterone supplementation or had LH levels ≥ 15 IU/L at baseline.

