10.2. Criteria for Potential Clinical Significant Abnormalities (PCSA)

Parameter	PCSA	Comments
Creatinine	≥150 µmol/L (Adults)	Benichou C., 1994.
	≥30% change from baseline	
	≥100% change from baseline	
CLcr (mL/min)	≥15 - <30 (severe	Use is optional.
(Estimated creatinine clearance	decrease in GFR)	FDA draft Guidance 2010
based on the Cokcroft-Gault equation)	≥30 - < 60 (moderate decrease in GFR)	Pharmacokinetics in patients with impaired renal function-study design, data analysis, and impact on dosing and labeling
	≥60 - <90 (mild decrease in GFR)	
	≥ 90 (normal GFR)	
eGFR (mL/min/1.73m2)	≥15 - <30 (severe	Use is optional.
(Estimate of GFR based on an	decrease in GFR)	FDA draft Guidance 2010
MDRD equation)	≥30 - < 60 (moderate decrease in GFR)	Pharmacokinetics in patients with impaired renal function-study design, data analysis, and impact on dosing and labeling
	≥60 - <90 (mild decrease in GFR)	
	≥ 90 (normal GFR)	
Uric Acid		Harrison- Principles of internal Medicine 17th Ed., 2008.
Hyperuricemia	>408 µmol/L	
Hypouricemia	<120 µmol/L	
Blood Urea Nitrogen	≥17 mmol/L	
Chloride	<80 mmol/L	
	>115 mmol/L	
Sodium	≤129 mmol/L	
	≥160 mmol/L	
Potassium	<3 mmol/L	FDA Feb 2005.
	≥5.5 mmol/L	
Lipasemia	≥3 ULN	
Amylasemia	≥3 ULN	
Glucose		
Hypoglycaemia	≤3.9 mmol/L and <lln< td="">ADA May 2005.	</lln<>	ADA May 2005.
Hyperglycaemia	≥11.1 mmol/L (unfasted); ≥7 mmol/L (fasted)	ADA Jan 2008.

Parameter	PCSA	Comments
HbA1c	>8%	
Albumin	≤25 g/L	
CRP	>2 ULN or >10 mg/L (if ULN not provided)	FDA Sept 2005.
Hematology		
WBC	<3.0 Giga/L (Non-Black); <2.0 Giga/L (Black)	Increase in WBC: not relevant. To be interpreted only if no differential count available.
	≥16.0 Giga/L	
Lymphocytes	>4.0 Giga/L	
Neutrophils	<1.5 Giga/L (Non- Black);<1.0 Giga/L	International Consensus meeting on drug-induced blood cytopenias, 1991.
	(Black)	FDA criteria.
Monocytes	>0.7 Giga/L	
Basophils	>0.1 Giga/L	
Eosinophils	>0.5 Giga/L or >ULN (if ULN≥0.5 Giga/L)	Harrison- Principles of internal Medicine 17th Ed., 2008.
Hemoglobin	≤115 g/L (Male); ≤95 g/L (Female)	Criteria based upon decrease from baseline are more relevant than based on absolute value. Other categories for decrease from
	≥185 g/L (Male); ≥165 g/L (Female)	baseline can be used (≥30 g/L, ≥40 g/L, ≥50 g/L).
	Decrease from Baseline ≥20 g/L	
Hematocrit	≤0.37 v/v (Male) ; ≤0.32 v/v (Female)	
	≥0.55 v/v (Male) ; ≥0.5 v/v (Female)	

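### SAP 5.8 counts HbA1c and hs-CRP PCSAs without the baseline-status split used for other laboratory tests, so the percentage mixes persisting with new abnormalities

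*SAP*

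**What the plan says.** The operative rule is in SAP 5.8. For HbA1c and hs-CRP it reads, in part: "Applying the PCSA criteria to these variables at any time during the TEAE period, the number of patients (and percentages) meeting the criteria". No baseline category is named. SAP 4.8 only points to the limits ("PCSA criteria for HbA1c are listed in Appendix 10.2").

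The limits in SAP Appendix 10.2 are absolute levels. HbA1c is flagged above 8%. The CRP entry is ">2 ULN or >10 mg/L (if ULN not provided". Neither has a change-from-baseline condition.

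For the other laboratory tests, SAP 5.7.2 counts patients with a post-baseline PCSA "while accounting for the baseline PCSA status (PSCA normal/missing; PCSA abnormal), for each patient group", and sends the version that ignores baseline status to the appendix. On layout it says: "These laboratory parameters will be presented by the biological functions defined in Section 4.7.2". The 4.7.2 list contains neither HbA1c nor hs-CRP; its metabolism line, for example, is "Metabolism: glucose, total protein, albumin, creatine phosphokinase".

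The common rules in SAP 5.7 do not add a split. They say that "PCSA criteria will determine which patients had at least 1 PCSA during the TEAE period", with a denominator "based on the number of patients assessed for that given parameter at least once during the TEAE period".

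**The concern.** A patient above a fixed limit before any PRALUENT, and above it again on treatment, is counted exactly like a patient who crosses the limit for the first time on PRALUENT. The first says something about who entered the study; only the second could point to deterioration. The study is uncontrolled, and both former treatment groups now receive PRALUENT, so no concurrent untreated rate is available to set against the combined figure.

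Glycaemic safety is a stated interest, since new-onset diabetes is an AESI. The SAP guards against this mixing elsewhere: laboratory PCSAs are split by baseline status, and the criteria for heart rate, blood pressure and weight require a change from baseline. As written, HbA1c and hs-CRP have neither protection, and the SAP gives no reason for the difference.

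**Working it through.** **1. Could a reader recover the split from other planned output?**

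- Baseline HbA1c categories (SAP 4.1) end at 6.5% and above, so the number above 8% at baseline is not tabulated. Baseline hs-CRP is not categorised.
- Change in HbA1c by visit (SAP 4.8) describes averages, not patients crossing a limit.
- New-onset diabetes (SAP 4.7.1.2) is assessed only in patients without diabetes, so it cannot show worsening in diabetic patients.
- Glucose PCSAs are split by baseline status (SAP 5.7.2), but glucose is a different measurement.
- SAP 5.8 also gives HbA1c summaries by diabetes status. Whether these include the PCSA count is unclear. If they do, a diabetic patient above 8% throughout and one who newly exceeds 8% still share a stratum.
- For hs-CRP no stratification is planned.

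**2. How much could the mixing matter?** The documents give no rate to reproduce and no HbA1c or hs-CRP distribution. The inputs below are therefore assumptions, except N = 1600, the expected enrolment in Protocol 6.1, which cancels out of the share.

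- b = share above the limit at baseline
- p = share of those who are above it again on treatment
- i = share of the remaining patients who newly exceed it

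Persisting = N·b·p. New = N·(1−b)·i. Persisting share = b·p / [b·p + (1−b)·i].

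Ranges: HbA1c b 2–10%, p 0.5–0.8, i 2–5%; hs-CRP b 2–10%, p 0.3–0.6, i 5–15%.

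| Case | b | p | i | Persisting | New | Total (% of 1600) | Persisting share |
|---|---|---|---|---|---|---|---|
| HbA1c, lowest share | 0.02 | 0.5 | 0.05 | 16.0 | 78.4 | 94.4 (5.9%) | 17% |
| HbA1c, intermediate | 0.05 | 0.8 | 0.02 | 64.0 | 30.4 | 94.4 (5.9%) | 68% |
| HbA1c, highest share | 0.10 | 0.8 | 0.02 | 128.0 | 28.8 | 156.8 (9.8%) | 82% |
| hs-CRP, lowest share | 0.02 | 0.3 | 0.15 | 9.6 | 235.2 | 244.8 (15.3%) | 4% |
| hs-CRP, highest share | 0.10 | 0.6 | 0.05 | 96.0 | 72.0 | 168.0 (10.5%) | 57% |

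The first two rows make the point best. Both print 5.9%, yet new occurrence among patients not above 8% at baseline is 78.4/1568 = 5.0% in one and 30.4/1520 = 2.0% in the other. The unsplit table cannot tell them apart. In the second case the split would show about 30 of 1520 new and 64 of 80 persisting.

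The hs-CRP ranges were chosen with 10 mg/L in mind. That is the fallback limit; the main one is twice the ULN, and SAP 4.7.2 says the central laboratory provides normal ranges. The real hs-CRP share could therefore differ.

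**3. Which baseline would the split use?** SAP 4.7 takes the last value before the first dose of study treatment unless otherwise noted. SAP 5.7 and 6.1 take the last value before double-blind treatment in the parent study. For former PRALUENT patients the parent-study value precedes all PRALUENT. For former placebo patients it does not capture what happened on placebo: a patient who crossed the limit on placebo and stayed above it would be classed as normal at baseline and shown as new on PRALUENT. Adding the split without settling the baseline would create a different misattribution.

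**The case against.** The strongest reply is that the absence of a split is inferred from silence. SAP 6.3 places missing baselines in a normal/missing category for PCSAs generally, without limiting this to certain parameters. Appendix 10.2 lists HbA1c and CRP among the chemistry tests, and Protocol 8.2.2.3 puts HbA1c under blood chemistry. The 5.7.2 sentence on biological functions describes layout and need not exclude anything. The programming team may well use the 5.7.2 shell for both tests.

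That possibility stands, and it is why the point is minor. It does not remove the point. SAP 5.8 states its own counting rule for these two variables without a split, and 6.3 only says where missing baselines go once a split exists.

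It is also fair to say that glycaemic deterioration does not rest on this count. New-onset diabetes, HbA1c change, glucose PCSAs and diabetes-related TEAEs by diabetic status all bear on it. The gap left is narrow: new crossings of 8% in diabetic patients, and new hs-CRP cases.

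Three stronger readings are tempting and not supported:

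- That everyone above the limit at entry is reported as an on-treatment abnormality. Such a patient counts only if a value in the TEAE period also meets the limit, so the figure is a genuine on-treatment prevalence.
- That the percentage would mainly describe who entered the study. The documents contain no distribution from which to show that, and the assumed ranges run well below and well above one half for HbA1c.
- That worsening glycaemia would go unseen. The analyses just listed cover much of it.

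**Conclusion.** The point holds as a minor one. Read as written, SAP 5.8 yields a single percentage for each variable that mixes persisting or recurring abnormalities with new ones, and no other planned table separates them for diabetic patients crossing 8% or for hs-CRP. The mixing follows from the text; its size does not. The 17% to 82% (HbA1c) and 4% to 57% (hs-CRP) ranges rest wholly on the assumed values of b, p and i. Early termination (SAP 1.1) makes them less certain still, because fewer on-treatment values than the full schedule could change both p and i. The consequence is limited: these are descriptive other variables, not the primary endpoint, and no test or decision depends on them.

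**What to change.** In SAP 5.8, state that HbA1c and hs-CRP PCSAs are tabulated by baseline PCSA status (normal/missing; abnormal) as in 5.7.2, with percentages based on the patients assessed within each baseline category. Keep the unsplit table for the appendix.

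In the same place, define baseline for these tables as the last value before the first PRALUENT dose: the parent-study baseline for former PRALUENT patients, and the open-label day 1 value, taken at the parent end-of-study visit, for former placebo patients. This also settles the difference between SAP 4.7 and SAP 5.7 for these tables.

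Extending the split to the gonadal-hormone tables of out-of-range values is optional. SAP 5.8 already repeats the hormone summaries with baseline exclusions, although it does not say explicitly that the out-of-range tables are repeated too.

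The cost is a sentence or two. The table layout already exists, and no new data are needed: Protocol Table 1 takes day 1 blood chemistry (which includes HbA1c) and hs-CRP from the parent end-of-study visit, and SAP 6.1 already provides for recovering parent-study data.

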4.9. Genomics Variables

Plans for analysis of genomics data will be provided in a separate SAP.

5. STATISTICAL METHODS

There will be no formal testing for safety variables. For the secondary efficacy endpoints, no formal statistical hypothesis will be tested.

Study data will be summarized descriptively for the following patient groups:

- The placebo treatment group (as-treated) in the neurocognitive function study (R727-CL-1532);
- The Praluent treatment group (as-treated) in the neurocognitive function study (R727-CL-1532);
- Overall: All patients in the safety population;

5.1. Demographics and Baseline Characteristics

Demographic and baseline characteristics will be summarized descriptively for the safety population. Parameters described in Section 4.1 will be summarized for the safety population.

The baseline value is generally defined as the baseline value in the neurocognitive function study (R727-CL-1532), i.e., the last available value before the first dose of double-blind study treatment in that study.

Continuous data will be summarized using the number of patients with data, mean, SD, median, minimum and maximum for each patient group. First quartile (Q1) and third quartile (Q3) will be also provided for baseline lipid parameters, HbA1c and hs-CRP. Categorical and ordinal data will be summarized using the number and percentage of patients in each patient group.

As applicable, other safety baseline data is presented collectively in the descriptive statistics summary tables containing respective post-baseline data.

5.2. Medical History and Disease Characteristics

Medical history and disease characteristics will be descriptively summarized. The medical history was not collected in this study. The medical history data from the neurocognitive function study (R727-CL-1532) will be used.

All reported patient's medical history and surgical history will be presented by primary SOC and HLT. The tables will be sorted by SOC internationally agreed order and decreasing patient frequency of HLT based on the overall incidence in the study. In addition, all medical

history of specific interest, as described in Section 4.2, will be summarized by patient incidence and percentage.

For the patients with primary CVD prevention status (see definition in Section 4.2), the number (and percentage) of patients with the following comorbidities/risk factors will be tabulated:

- Diabetes mellitus with target organ damage (renal damage (microalbuminuria, or macroalbuminuria, moderate CKD) and/or retinopathy (pre-proliferative or proliferative diabetic retinopathy and/or laser treatment for diabetic retinopathy)),
- Diabetes mellitus with 2 or more risk factors (see Section 4.2),
- Family History of premature CHD
- Hypertension,
- Moderate CKD
- Current smoker
- At least 2 of the above comorbidities/risk factors

In addition, smoking status will be summarized in patients with primary CVD prevention status.

For the patients with a secondary prevention status, the CVD history will be described using the number (%) of patients with:

- History of CHD (see Section 4.2)
- History of ischemic stroke
- History of PAD with severity criteria
 - Intermittent claudication and ankle brachial index ≤ 0.90
 - Peripheral revascularization procedure (angioplasty, stenting) for PAD
 - Thrombolysis for PAD
 - Peripheral revascularization surgery (arterial bypass) for PAD
 - Critical limb ischemia

Additionally:

CONFIDENTIAL

- The number (%) of patients with a secondary prevention status with 1 or more associated comorbidity among hypertension, diabetes mellitus, and/or moderate CKD will be summarized.
- The number (%) of patients with history of CHD and 1 or more associated comorbidity among hypertension, diabetes mellitus, moderate CKD and/or other CVD (ischemic stroke, PAD) will be summarized.

For patient disease characteristics, as described in Section 4.2, continuous data will be summarized using the number of patients with data, mean, SD, median, minimum and maximum for the study and for each of the strata. Categorical and ordinal data will be summarized using the number and percentage of patients in the study.

